### 10.1. Serum or Plasma Hormone Measurements

Descriptive statistics will be presented by treatment group and visit for the observed and change from OL baseline values for the following serum or plasma hormone measurements in the OL period: ACTH, 17-OHP, androstenedione, testosterone, cortisol, LH, and FSH. Summaries of testosterone, LH, and FSH will be stratified by sex and Tanner stage (breast or testicular Tanner stages 1, 2 vs. Tanner stages 3-5). Visits where the hormone measurement is collected more than once will be handled as described in Section 9.6.1. Observed and change from timepoint-matched OL baseline sample will be summarized for pre-morning GC dose values and visit average values.

Mean (±SEM) values of the above hormone measurements at each visit in the OL period will be summarized in line graphs by treatment group. Pre-morning GC dose values and average values will be presented on separate plots. Similar graphs will be presented for the changes from OL baseline.

The above summaries will be repeated for the change from baseline to Week 52 in each of the hormone parameters.

A responder definition for the normalization of testosterone in female subjects will be defined as female subjects with testosterone levels that are greater than or equal to 1.2x ULN (based on age) at OL baseline and decrease to within the normal range at any post-OL baseline visit. Descriptive statistics will be presented by treatment group for the number and percentage of female subjects classified as responders at each visit in the OL period.

A responder definition for the ratio of androstenedione to testosterone (A4/T) in male subjects (Tanner stage 2 [testicular] and above) will be defined as male subjects who have A4/T greater than or equal to 0.5 (based on the pre-glucocorticoid dose values for androstenedione and testosterone) at OL baseline and who achieve A4/T less than 0.5 at any post-OL baseline visit thereafter. Descriptive statistics will be presented by treatment group for the number and percentage of male subjects classified as responders at each visit thereafter in the OL period.

# **10.2.** Salivary Hormone Measurements

Descriptive statistics will be presented by treatment group and visit for the observed and change from OL baseline values for the following salivary hormone measurements in the OL period: 17-OHP, androstenedione, testosterone, progesterone, pregnenolone, and cortisol. Visits where the hormone measurement is collected more than once will be handled as described in Section 9.6.2. Observed and change from timepoint-matched OL baseline will be summarized for pre-dose values and mean 24-hour values. Summaries of testosterone, progesterone, and pregnenolone

will be stratified by sex and Tanner stage (breast or testicular Tanner stages 1, 2 vs. Tanner stages 3-5).

Mean (±SEM) values of the above salivary hormone measurements at each visit in the OL period will be summarized in line graphs by treatment group. Pre-dose values and visit average values will be presented on separate plots. Similar graphs will be presented for the changes from OL baseline.

The above summaries will be repeated for the change from baseline to Week 52 in each of the hormone parameters.

# 10.3. Glucocorticoid Total Daily Dose

Descriptive statistics will be presented by treatment group and visit for the glucocorticoid total daily dose (mg/m^2/day) observed, change from OL baseline, and percent change from OL baseline values to Week 52. Mean ( $\pm$ SEM) values of the glucocorticoid total daily dose (mg/m^2/day) at each visit will be summarized in line graphs by treatment group. Similar graphs will be presented for the change from OL baseline and percent change from OL baseline. These summaries will be presented for both the glucocorticoid total daily doses *without* the derivation of 0 for loss of androstenedione control as well as the glucocorticoid total daily doses *with* the derivation of 0 for loss of androstenedione control (only for subjects with a decrease in glucocorticoid total daily dose).

The above summaries will be repeated for the change from baseline to Week 52 in glucocorticoid total daily dose.

Similar to the responder analysis defined in Section 9.5.1, a physiologic glucocorticoid dose responder will be defined as the achievement of a reduction in glucocorticoid total daily dose to physiologic levels ( $\leq 11 \text{ mg/m}^2$ /day hydrocortisone equivalent adjusted for BSA) at OL period visits through Week 52, while androstenedione is adequately controlled at  $\leq 120\%$  of baseline or  $\leq$ ULN for age and sex, respectively, at each given visit. Androstenedione control will be assessed based on the androstenedione values at study baseline and each respective OL period visit through Week 52 following the same method as described in Section 6.3.3. Descriptive statistics will be presented by treatment group for the number and percentage of subjects classified as responders and non-responders at each visit in the OL period.

# 10.4. Metabolic Assessments

Descriptive statistics will be presented by treatment group and visit for the observed and change from OL baseline values for the following metabolic assessments: HOMA-IR, total cholesterol, LDL, triglycerides, and HDL.

The above summaries will be repeated for the change from baseline to Week 52 in each of the metabolic assessments.

# 10.5. Bone Age

The change from baseline to Week 52 in the ratio of bone age to chronological age (BA:CA) will be summarized with descriptive statistics by treatment group in the subgroup of subjects not at adult height (female subjects with the most recent prior bone age <14 years and males with the

most recent prior bone age <16 years) and not on gonadotropin-releasing hormone agonist therapy, growth hormone therapy, or aromatase inhibitors at study entry. BA:CA will be calculated at baseline and Week 52 by taking the bone age and dividing it by the chronological age of the subject at each respective timepoint.

The change from baseline to Week 52 in the difference in bone age and chronological age (BA-CA) will also be summarized with descriptive statistics by treatment group.

The above summaries will be repeated for the change from OL baseline to Week 52.

## 10.6. Bayley-Pinneau Predicted Adult Height SDS

The change from baseline in Bayley-Pinneau predicted adult height SDS at Week 52 is a secondary endpoint, which will be analyzed using an ANCOVA model, as described in Section 9.2.1. Bayley-Pinneau predicted adult height SDS will be determined at baseline and Week 52 using the height and bone age of the subject at these respective visits as described in Section 9.6.7.

Descriptive statistics and LS means for change from baseline to Week 52 in Bayley-Pinneau predicted adult height SDS will be presented by treatment group (from the double-blind period) along with the LS-mean treatment difference, 95% confidence intervals, and p-value.

## 10.7. Growth

In subjects not at adult height (female subjects with the most recent prior bone age <14 years and males with the most recent prior bone age <16 years at study entry) and not on gonadotropin-releasing hormone agonist therapy, growth hormone therapy, or aromatase inhibitors at study entry, height SDS and height velocity (cm/year) will be summarized with descriptive statistics by visit and treatment group.

Height velocity will be calculated in subjects not at adult height. OL baseline will be calculated as the difference in height at Week 28 and height at study baseline, divided by the number of days between both measurements. Height velocity at Week 52 will be calculated as the difference in height at Week 52 and Week 28, divided by the number of days between both measurements. If height is missing at Week 28, the last measured height prior to Week 28 will be used. All height velocity values will be converted to cm/year. Change from OL baseline to Week 52 in height velocity will be summarized with descriptive statistics by treatment group.

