#### Neurocrine Biosciences, Inc., Study No. NBI-74788-CAH2006 Clinical Protocol Amendment No. 3 Final Version

- a The screening period can be extended by up to 4 weeks after discussion with and approval of the Medical Monitor to allow for delayed screening laboratory results that are needed to determine eligibility or to accommodate other extenuating logistical issues, such as scheduling. The Week 4 visit will have a visit window of ±5 days, and subsequent visits through Week 52 will have a visit window of ±7 days. The Week 56 visit (if applicable) visit has a visit window of +7 days. All Week 28 assessments should be completed before a subject begins open-label treatment. Not all assessments must be conducted on the same day, but all assessments for a given visit must be completed within the visit window. If a subject's GC regimen is adjusted due to stress dosing, the subject should resume their GC dosing regimen for at least 3 days before their next scheduled lab test if the duration of stress dosing is 3 days or less, and for at least 7 days before their next scheduled lab test if the duration of stress dosing is ≥4 days (this 3- or 7-day window supersedes all other visit windows).
- b At home or the study site. At Week 16 and Week 40, at home is an option if height is not required. During the screening period, blood and urine collection may be arranged at home.
- c Only if a preceding GC dose adjustment occurred.
- d Subjects will have further GC adjustment starting at Week 32 only if their Week 32 GC dose is >11 mg/m^2/day.
- c For subjects who discontinue the study prior to Week 52, assessments will be performed at the ET visit and at the safety follow-up visit, consisting of the same procedures as shown for Week 56 in the schedule of assessments. A safety follow-up visit is not required if the last dose of study drug was at least 4 weeks prior to the ET visit. Subjects who complete the Week 52 visit and elect to not enter the OLE will undergo a safety follow-up visit approximately 4 weeks after last dose of study drug.
- f Only for subjects age ≥12 years of age.
- Tanner stage at screening and Day 1. Historical assessment of Tanner staging is acceptable if Tanner stage 5 has been previously documented. Tanner staging at subsequent visits is required only if baseline Tanner stage <5. In addition, subjects with Tanner stage 4 at baseline do not need to undergo Tanner staging at Week 16 or Week 40.

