- h Measure blood pressure 3 times, in up to 1-minute intervals, after the subject has been sitting quietly for at least 5 minutes. Measure weight with subjects not wearing shoes or outerwear (eg, jackets or coats). Measure height (in subjects not wearing shoes) as the average of 3 to 6 measurements using a stadiometer (or length board) (Section 9.3.3). Height not required at Week 4 or Week 56 (all subjects) or at Week 16 and Week 40 if growth <2.5 cm in past year, complete fusion of epiphyses on hand/wrist radiograph, or more than 2 years past menarche (females).
- Only for females of childbearing potential. Serum pregnancy testing at screening, urine pregnancy tests at other visits.
- j Blood samples for A4, 17-OHP, and ACTH will be collected:
- For subjects who are  $\ge 6$  years of age with a body weight  $\ge 20$  kg: On Day 1 and Week 4 approximately 15 minutes before and just prior to dosing with the morning GC and (Week 4) study drug between approximately 0800 and 0830 hours and at 2, 3, 4, and 6 hours after dosing. Any midday GC dose the subject is receiving should be taken after blood is sampled 6 hours after dosing.
- For subjects who are ≥6 years of age with body weight ≥20 to <30 kg: only a single sample for ACTH will be collected, which will be the sample just prior to the morning GC dose.
- For subjects who are <6 years of age or with a body weight <20 kg: collect a blood sample prior to dosing with the morning GC, (if applicable) fludrocortisone, and (Week 4) study drug, with dosing between approximately 0800 and 0830 hours.

All subjects should take their GC dose the night before prior to 2100 hours.

- k For all subjects, a blood sample for PK prior to the morning study dose will be collected at Weeks 4, 16, 28, 40, and 52/ET, if ET occurs prior to Week 52. At Week 4: for subjects who are ≥6 years of age with a body weight ≥30 kg, blood samples for PK will also be collected approximately 2, 3, 4, and 6 hours after dosing.
-  Salivary samples for adrenal androgens and precursors will be collected:

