#### 9.3.3. Height and Body Weight

Height will be measured using a wall-mounted stadiometer in a subject without shoes, while instructed to stand tall with feet flat on the floor, heels against the wall, and looking straight forward. Subjects less than 3 years of age may be measured with a length board, but all measurements during the study should be made with the same technique (stadiometer or length board). Measurements should be recorded to the nearest 0.1 cm as the average of 3 to 6 independent measurements, each recorded to the nearest 0.1 cm. Height will be measured (using a stadiometer or length board) in all subjects during screening and at Day 1, Week 28, Week 52, Month 18 and every 6 months thereafter, and at early termination. Subjects who have grown less than 2.5 cm within the past year, have complete fusion of epiphyses on the hand/wrist radiograph, or are more than 2 years past menarche (females) are not required to have height measurement at Week 16 or Week 40. Height will be expressed in cm and in standard deviation scores (SDS) according to the Center for Disease Control (CDC) growth charts.

Weight will be measured using a digital scale as the average of 3 measurements and recorded to the nearest 0.1 kg with subjects not wearing shoes or outerwear (eg, jackets or coats). Weight will be expressed in kg and in SDS according to CDC growth charts.

Body mass index will be calculated as weight divided by height squared (kg/m²) and expressed in SDS according to CDC growth charts.

BSA based on weight and height will be calculated using the DuBois Method.

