Week 16	112	99 to 126
Week 20	140	127 to 168
Week 28	196	169 to (first dose date in OL period)
Week 32	224	(First dose date in OL +1) to 238
Week 36	252	239 to 266
Week 40	280	267 to 294
Week 44	308	295 to 336
Week 52	364	337 to (first dose date in OLE or Week 56)

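### When the Week 28 height is missing, SAP 10.7 starts the open-label height velocity from an earlier double-blind height, so in those children the two periods being compared are mixed

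*SAP*

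**What the plan says.** SAP 10.7 (Growth) defines two velocities for children not at adult height, each converted to cm/year.

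- Double-blind velocity, which serves as the baseline for the comparison: "OL baseline will be calculated as the difference in height at Week 28 and height at study baseline", divided by the days between the two measurements.
- Open-label velocity: "Height velocity at Week 52 will be calculated as the difference in height at Week 52 and Week 28, divided by the number of days".

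The change from the first to the second is summarised descriptively by treatment group. The fallback for both is: "If height is missing at Week 28, the last measured height prior to Week 28 will be used". The section sets no limit on how old the substituted height may be and plans no sensitivity summary.

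Protocol Table 7 schedules only one height between Day 1 and Week 28, at Week 16. Its footnote h reads "Height not required at Week 4 or Week 56 (all subjects) or at Week 16 and Week 40 if growth <2.5 cm in past year", and it also exempts children with fused epiphyses or more than 2 years past menarche. Protocol 9.3.3 repeats that these children "are not required to have height measurement at Week 16 or Week 40".

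In SAP 6.7, Table 4 sets the Week 28 analysis window at Day "169 to (first dose date in OL period").

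**The concern.** The comparison is meant to set growth before open-label crinecerfont against growth on it. All subjects move to active drug on the evening of the Week 28 visit (Protocol 7.3), so the boundary between the intervals should lie there. Under the fallback, the boundary moves back to the earlier height for both velocities. Dividing by the actual number of days keeps the time scale right but does not undo the mixing: the interval labelled open-label now includes weeks from the double-blind period. In the placebo/crinecerfont group those weeks were on placebo, and that is the group in which a before/after change would be read as an effect of starting the drug.

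The SAP keeps the periods apart elsewhere. The parallel change in menstrual rate (SAP 10.9) counts cycles within each period and divides by the days in that period.

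**Working it through.** The documents state no figure on this point, so there is none to reproduce.

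**Inputs.** Target days from SAP Table 4: Week 16 = 112, Week 28 = 196, Week 52 = 364. Day 1 is taken as about day 0. Visit tolerance from Protocol Table 7, footnote a: "subsequent visits through Week 52 will have a visit window of ±7 days". The growth velocities below are assumptions for illustration.

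**1. Share of time.** If the substituted height is from day *d*, the double-blind share of the open-label interval is (196 − *d*)/(364 − *d*).

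- Week 16 height: (196 − 112)/(364 − 112) = 84/252 = 33.3%.
- All three visits shifted by up to 7 days: lowest (189 − 119)/(371 − 119) = 70/252 = 27.8%; highest (203 − 105)/(357 − 105) = 98/252 = 38.9%.
- Same, but with Week 16 anywhere in its SAP analysis window (Day 99 to 126): lowest 63/245 = 25.7%; highest 104/258 = 40.3%.

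**2. Effect on the change, steady double-blind velocity.** Let the double-blind velocity be *D* and the open-label velocity *O*. The open-label velocity under the rule is (84*D* + 168*O*)/252 = *D*/3 + 2*O*/3. Subtracting *D* gives (2/3)(*O* − *D*).

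- 6 then 8 cm/year: true +2.00, reported +1.33.
- 7 then 5 cm/year: true −2.00, reported −1.33.

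**3. Effect on the change, unsteady double-blind velocity.** Let velocity be *a* to Week 16, *b* from Week 16 to Week 28, and *c* on open-label drug. The intended change is *c* − (112*a* + 84*b*)/196 = *c* − (4*a* + 3*b*)/7. The change under the rule is (*b* + 2*c*)/3 − *a*.

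| *a*, *b*, *c* (cm/year) | Intended change | Under the rule |
|---|---|---|
| 5, 4, 6 | 6 − 32/7 = +1.43 | (4 + 12)/3 − 5 = +0.33 |
| 5, 6, 6 | 6 − 38/7 = +0.57 | (6 + 12)/3 − 5 = +1.00 |

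The first row understates the change and the second overstates it.

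**4. Only a Day 1 height available.** The baseline velocity becomes (H − H)/0 days, which is undefined. No change can be formed.

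**5. Effect on a group mean.** If a fraction *f* of the group is affected, with the same mean change as the rest and steady double-blind velocity, the mean change is reduced by *f*/3. The documents do not give *f*. Over an assumed range: 2% gives 0.7%, 5% gives 1.7%, 10% gives 3.3%, 20% gives 6.7%.

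**The case against.** The strongest reply is that very few children, perhaps none, will be affected. Open-label efficacy summaries use only subjects who took an open-label dose (SAP 10 and Table 1), so children who leave during the double-blind period never enter. Height at Week 28 has no exemption (Protocol 9.3.3). Week 28 assessments should be finished before open-label treatment begins, and the same height feeds the body-surface-area adjustment of the second key secondary endpoint. The case needs a child who started open-label drug with no height in a window that opens at Day 169. This stands, and it is why the point is minor. It does not make the rule right when it is used. The window also closes at the first open-label dose, so a height taken a few days late is not a Week 28 value and the rule reaches back. Bone age, by contrast, is allowed 28 further days (SAP Table 6).

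A second reply is that SAP 6.3.2 already handles the Day 1 case. Its general open-label baseline rule appears to bar the study-baseline value, and it leaves out assessments taken only at Day 1 and Week 28 when Week 28 is absent. The first sentence is not cleanly legible in the text available, which is not held against the plan. The second does not plainly cover height, which most growing children also have at Week 16. Section 10.7 repeats neither limit, so the two sections need to be reconciled. Children exempt at Week 16 should be uncommon in the analysed subgroup, which is limited by bone age.

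A third reply is that children randomised to crinecerfont, the larger group under 2:1 allocation, take active drug in both periods. That is correct: for them the periods are mixed but the treatment is not.

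**Conclusion.** The rule as written gives a wrong open-label velocity in any child to whom it applies, and an undefined baseline velocity if the only earlier height is from Day 1. With a Week 16 height, about one third of the interval's time is double-blind. The two-thirds attenuation rests on a steady velocity from Day 1 to Week 28.

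Three stronger readings are tempting and are not supported.

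- A reader might infer that the change always shrinks. It need not: glucocorticoid doses are adjusted from Week 4 to Week 28, so steady growth is not assured, and the 5, 6, 6 example inflates the change.
- A reader might infer that a third of the growth is misattributed. One third is a share of time. With 5 then 6 cm/year the share of growth is 84 × 5/(84 × 5 + 168 × 6) = 29.4%; with 6 then 5 it is 37.5%.
- A reader might take the Day 1 fallback, where 196/364 = 54% of the time would be double-blind, as a more severe dilution. It produces no change value at all, and 6.3.2 appears to rule it out.

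The endpoint is exploratory (SAP 4.5) and untested. No primary or key secondary result and no type I error statement is touched.

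**What to change.** Replace the fallback sentence in SAP 10.7 with:

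> If no height is available in the Week 28 window before the first open-label dose, the last double-blind height after Day 1 (Week 16) may be used only for the double-blind (OL-baseline) velocity. The Week 52 (open-label) velocity and the change from OL baseline are set to missing, and the number of subjects affected is reported. The Day 1 height is never used as the Week 28 height.

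Word 6.3.2 to agree. This brings the double-blind share of the open-label interval to zero.

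A Week 40 to Week 52 velocity could be shown as a sensitivity summary, but it is not a good replacement. Annualising over 12 weeks multiplies height measurement error by 52/12 = 4.33, against 52/24 = 2.17 over the planned 24 weeks, and the Week 40 height has the same exemptions as Week 16.

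The cost is one SAP sentence, a matching edit to 6.3.2, and the loss of a few children from a descriptive summary. No study procedure changes.

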## 10.8. Body Weight and BMI

Descriptive statistics will be presented by treatment group and visit for the observed and change from OL baseline values for body weight SDS and BMI SDS.

The above summaries will be repeated for the change from baseline to Week 52.

In the subset of subjects classified as overweight or obese (BMI  $\ge 85^{\text{th}}$  percentile at OL baseline), the number and percentage of subjects achieving normal weight (BMI <  $85^{\text{th}}$  percentile) at Week 52 will also be presented by treatment group.

### 10.10. TARTs

Change from baseline to Week 52 in TARTs will also be summarized for the OL period in male subjects with TARTs at baseline. For the purpose of summarization, the volume of each lesion will be used to assess size (in cubic millimeters) at visits where the testicular ultrasound is performed. Volume will be calculated using the following formula: volume = length x width x depth x 0.5236. The volume of each testicle will be calculated using the same formula. Descriptive statistics will be used to summarize the total TART volume (calculated as the sum of the volume of each lesion across both testes) for each subject by treatment group and visit. Observed and change from baseline values will be included in the summary table.

Additionally, the total TART volume will be expressed as a percentage of the total testicular volume and calculated as the sum of the volume of each lesion across both testes divided by the total testicular volume across both testes for each subject. The total TART volume as a percentage of the total testicular volume will be summarized with descriptive statistics by treatment group and visit. Observed and change from baseline values will be included in the summary table.

The number and percentage of subjects with the presence of TARTs, whether they are unilateral or bilateral, and the average number of TARTs per subject will be summarized with descriptive statistics by visit and treatment group. The number and percentage of TARTs with each shape, boundary, hypervascularity, calcification, and echogenicity will be summarized with descriptive statistics by treatment group.

A response assessment will be conducted at Week 52 for subjects with the presence of TARTs at baseline. Response categories and the criteria for each category are detailed in Table 7 within

Section 9.6.4. The frequency and percentage of subjects meeting each classification at Week 52 (as compared to baseline) will be summarized by treatment group.

